12 OCT2020

### **8.3.5. Packaging and Labeling of AP01 and Nebulizer Kits**

#### AP01 IP Supply

Overwrapped AP01 IP ampoules will be packaged and labelled as required by regional regulation by PPD Development, L.P. in Athlone, Ireland. Each IP carton will contain 18 AP01 overwrapped pouches, each pouch containing two ampoules. Each ampoule will contain 4 mL AP01 12.5 mg/mL formulation, which is a 50 mg dose. The 50 mg once daily inhaled dose cohort will use one IP carton every 4 weeks (1/2 pouch per day; 1 ampoule per once daily dose). The 100 mg twice daily inhaled dose cohort will use four IP cartons every 4 weeks (2 pouches per day; 2 ampoules per twice daily dose). Details of IP distribution will be outlined in the clinical study manual.

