## **8.8. Investigational Drug Accountability, Handling and Disposal**

### **8.8.1. Investigational Drug Handling and Disposal**

Administration of the first dose of IP will be observed by the investigator or designee; time of administration and confirmation of full dose being administered will be noted on the eCRFs.

The investigator or designee is responsible for IP and accountability, reconciliation and record maintenance. In accordance with all applicable regulatory requirements, designated research or pharmacy staff at each study site must maintain IP accountability records for study drug throughout the course of the study.

Patients will be instructed to bring back the box(es) of unused ampoules at each study visit for drug accountability purposes. Patients will be instructed to dispose of all used ampoules. Details regarding drug accountability procedures will be captured in the clinical study manual.

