### **8.9.2. Treatment Compliance**

Administration of the first dose of IP will be observed by the investigator or designee; time of administration and confirmation of full dose being administered will be noted in the eCRF. Patients will bring all unused ampoules to each visit for drug accountability and compliance assessment. At the discretion of the investigator, patients that are not in compliance with study dosing and procedures will be discontinued from the study.

Avalyn Pharma, Inc.  
AP01-002

Protocol V2.1  

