then subtracted from the time of nebulization. Time of nebulization will then be summarized for each dose by treatment group with descriptive statistics. In addition, the Time of nebulation will be summarized for just those patients who took the full dose with no interruptions for each dose by treatment group with descriptive statistics.

- To assess tolerance, the number of patients with a $\geq 15\%$ drop from pre-dose FEV₁ % predicted to post-dose FEV₁ % predicted will be summarized for each dose (first dose only if only 1 dose was received or for each dose if 2 doses are received) by treatment group with frequency counts and percentages (see more details in Section 10.6).

Post-Baseline: At Home

- For each patient, the treatment days will be derived cumulatively across all visits as the last dose date minus the first dose date + 1 and will be summarized by treatment group with descriptive statistics.
- For each patient, the actual total dosage (mg) of AP01 will be derived cumulatively across all visits across all patient doses as 50 times the total number of used ampoules returned, and will be summarized by treatment group with descriptive statistics.
- For each patient, the percent compliance will be derived cumulatively across all visits across all patient doses as 100 times (the total number of used ampoules returned divided by the total number of ampoules that would be used if they were fully dosing for the number of days between visits {slightly different from the number of ampoules dispensed}). If a subject discontinues early, the denominator will be the total number of ampoules, which would be used up to, and including the date of discontinuation. Percent compliance will be summarized by treatment group with descriptive statistics. The percent compliance will be categorized ($\geq 80\%$, 60- $<80\%$, 40- $<60\%$, 20- $<40\%$ and $<20\%$) and summarized by treatment group with frequency counts and percentages. The percent compliance will be calculated overall and separately for each dosing regimen for those patients who switch over from 50 mg once daily to 100 mg twice daily in Part B.

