- For each patient, the percent compliance with the patient's care plan will be derived cumulatively across all visits across all patient doses as 100 times (the total number of used ampoules returned divided by the total number of ampoules that would be used if they were fully dosing for the number of days between visits minus the number of ampoules that would be missed if following instructions to reduce or interrupt dose). If a subject discontinues early, the denominator will be the total number of ampoules, which would be used up to, and including the date of discontinuation. Percent compliance will be summarized by treatment group with descriptive statistics. The percent compliance will be categorized ($\geq 80\%$, 60- $<80\%$, 40- $<60\%$, 20- $<40\%$ and $<20\%$) and summarized by treatment group with frequency counts and percentages. The percent compliance will be calculated overall and separately for each dosing regimen for those patients who switch over from 50 mg once daily to 100 mg twice daily in Part B.
- The number of patients who had any days where all doses were missed will be summarized cumulatively across all visits by treatment group with frequency counts and percentages. For those patients who had any days where all doses were missing, the maximum number of days between doses will be summarized cumulatively across all visits by treatment group with descriptive statistics.

This document is confidential.

SAP Version: 3.0 (15JUL2021)
Controlled Document ID: **3903A.01**, Effective Date 29-Oct-2018
Filing requirements: TMF

Page 28 of 52

Statistical Analysis PlanSponsor: Avalyn Pharma, Inc.; Protocol No.: AP01-002

All recorded information for study medication administration and accountability for AP01 will be listed.

All recorded information for Nebulizer Training, Nebulizer and Nebulizer handset accountability will be listed.

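### SAP 7.5 counts used ampoules returned, but the protocol has patients discard them, so at-home dosage and both compliance percentages are invalid or not derivable as written

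*SAP*

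**What the plan says.** SAP 7.5, in the part on post-baseline dosing at home, defines three variables from one count:

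- Actual total dosage in mg "will be derived cumulatively across all visits across all patient doses as 50 times the total number of used ampoules returned".
- Percent compliance is 100 times "the total number of used ampoules returned divided by the total number of ampoules that would be used if they were fully dosing" over the days between visits.
- For care-plan compliance, "the percent compliance with the patient's care plan will be derived cumulatively across all visits across all patient doses as 100 times" a ratio with the same numerator. Its denominator is reduced by the ampoules that an instructed dose reduction or interruption would leave unused.

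Both percentages are also sorted into five categories, the lowest being below 20%. Both are repeated by regimen for patients who move from 50 mg once daily to 100 mg twice daily in Part B.

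The protocol describes a different flow of ampoules. Section 8.8.1 says "Patients will be instructed to dispose of all used ampoules" and "Patients will be instructed to bring back the box(es) of unused ampoules at each study visit for drug accountability purposes". Section 8.9.2 rests the compliance assessment on the same material: "Patients will bring all unused ampoules to each visit for drug accountability and compliance assessment". Further accountability detail is left to the clinical study manual.

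SAP section 12 lists one change from the protocol, the addition of the Full Analysis Set. It does not mention ampoule counting.

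**The concern.** The SAP counts what the protocol tells patients to throw away, and the protocol collects what the SAP formulas do not use. A patient who follows instructions contributes nothing to the numerator. A patient who returns used ampoules against instructions gets credit, so the score would partly measure failure to follow the disposal instruction.

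What is at stake is the description of exposure. Protocol 8.2 expects the shorter, once-daily regimen to improve compliance, and these summaries are where a reader would look for that. Assigned arm alone does not show dose taken, because Protocol 8.7 allows reductions and interruptions and Part B includes a regimen switch.

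**Working it through.** **Inputs**

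- Content of an ampoule (Protocol 8.3.5): "Each ampoule will contain 4 mL AP01 12.5 mg/mL formulation, which is a 50 mg dose".
- Carton size (Protocol 8.3.5): "Each IP carton will contain 18 AP01 overwrapped pouches, each pouch containing two ampoules", so 18 × 2 = 36 ampoules.
- Ampoules per day (Protocol 8.3.5): 1 on 50 mg once daily; 2 pouches = 4 on 100 mg twice daily.
- Part A: 24 weeks × 7 = 168 days.
- Used ampoules returned when the protocol is followed: 0, or not recorded.

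**1. The plan's own supply figure.** The documents give no exposure or compliance figure, but Protocol 8.3.5 states cartons per 4 weeks.

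- 50 mg once daily: 28 × 1 = 28 ampoules; 28/36 = 0.78, so 1 carton, as stated.
- 100 mg twice daily: 28 × 4 = 112 ampoules; 112/36 = 3.11, so 4 cartons, as stated.

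Supply per 4 weeks is therefore 36 and 144 ampoules. Full adherence leaves 36 − 28 = 8 and 144 − 112 = 32 unused.

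**2. True use at full adherence over Part A**

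| Regimen | Ampoules | Dosage |
|---|---|---|
| 50 mg once daily | 168 × 1 = 168 | 168 × 50 = 8,400 mg |
| 100 mg twice daily | 168 × 4 = 672 | 672 × 50 = 33,600 mg |

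These totals include the Day 1 dose given in clinic. Without that dose they are 168 − 1 = 167 and 672 − 2 = 670 ampoules.

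**3. The SAP formulas under the protocol's return rule.** If the field holds zero, dosage is 50 × 0 = 0 mg and compliance is 100 × 0/28 or 100 × 0/112 = 0%, whatever the true adherence. If the field is blank, all three variables are missing. If 5% or 10% of used ampoules came back anyway (an assumed range), a fully adherent patient would score 5% or 10%.

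**4. Dispensed minus unused returned, per 28 days at full adherence**

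- 50 mg once daily: 36 − 8 = 28; 28 × 50 = 1,400 mg; 28/28 = 100%.
- 100 mg twice daily: 144 − 32 = 112; 112 × 50 = 5,600 mg; 112/112 = 100%.

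At an assumed 80% adherence on 50 mg once daily, 22.4 ampoules are used and 13.6 come back, so (36 − 13.6)/28 = 80%. At an assumed 60%, the result is 60%. The other arm gives the same percentages.

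**5. A substitution to avoid.** If unused ampoules were entered as the numerator, full adherence would score 8/28 = 32/112 = 28.6%. The score would rise as adherence fell: 13.6/28 = 48.6% at 80% adherence and 19.2/28 = 68.6% at 60%.

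**6. Boxes not brought back.** Take a fully adherent patient with six nominal 28-day intervals on 50 mg once daily and two boxes missing. Removing those intervals from the numerator only gives 112/168 = 66.7%, which drops the patient from the top category (80% or more) to the next. Removing them from both sides gives 112/112 = 100%. Counting every unreturned ampoule as used in an interval gives 36/28 = 144/112 = 128.6%, because of the overage in step 1.

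**The case against.** A reader might infer from step 3 that reported exposure and compliance will come out near zero, and that the safety findings or the comparison of regimens are therefore compromised. The documents do not support either inference.

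On the first, neither the eCRF nor the clinical study manual is among the documents. The field may be blank, or may hold a used count derived by the site. SAP 7.5 also plans summaries of days on which all doses were missed and of the longest gap between doses. Return counts cannot supply these, so some other dosing record seems to be presupposed. A programmer might also sensibly use dispensed minus unused. What stands is that the SAP specifies none of this, and that its wording asks for a count the protocol does not produce.

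On the second, the three variables are descriptive. The Safety Set requires one dose. Per-Protocol exclusion refers to major deviations, including study drug deviations, with no link to a calculated percentage. Compliance is not a covariate in the FVC model. Part B entry and site compliance decisions rest on the investigator's judgement. Treatment days come from dose dates, and the clinic dose comes from nebulizer volume. This objection stands in full and limits the importance of the point.

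**Conclusion.** The contradiction is real, and neither document resolves it. For patients who follow the protocol, the numerator of total dosage, percent compliance and care-plan compliance is zero or missing, so these outputs are invalid or not derivable as written. The use left uncounted at full adherence in Part A is 8,400 mg and 33,600 mg in the two arms.

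This should be fixed, but it does not threaten the main results: the FVC analyses, adverse event summaries, analysis sets, treatment days and in-clinic dose are unaffected. What is lost is the exposure and adherence context for reading them. The conclusion assumes that the protocol's return instruction is the one in force and that the study manual does not override it.

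**What to change.** In all three formulas of SAP 7.5, replace the count of returned used ampoules by ampoules dispensed minus unused ampoules returned. Then add two rules:

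- Where the box for an interval is not brought back, remove that interval from both numerator and denominator. Total dosage has no denominator, so report it with the number of days it covers.
- In any sensitivity run that counts unreturned ampoules as used, cap the count at the number expected for that interval, since 36 ampoules are supplied for 28 needed (144 for 112).

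Record the clarification in the SAP. The cost is SAP wording and programming, on the assumption that dispensed and unused-returned counts are captured in the accountability data. The protocol's return instruction and the accountability listing planned in SAP 7.5 make that likely but do not prove it. If the study manual does have used ampoules returned, Protocol 8.8.1 and 8.9.2 must be reconciled with it instead.

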## **8.7. Missed Doses and Dose Modifications**

Doses that are missed can be taken in a 24-hour period, as long as doses are 4 hours apart.

In the event of excessive coughing while drug administration at home, the patient will contact the site to determine how to proceed. Salbutamol may be prescribed to be administered prior to dosing, as described in section 8.6, if deemed necessary by the investigator.

If AP01 is stopped during treatment due to intolerance, restart dosing when the patient has improved. The initial dose after restarting should be observed for tolerance.

It is recommended to reduce the 100 mg twice daily dose to 50 mg twice daily if the patient cannot tolerate the 100 mg dose. If the 50 mg twice daily dose cannot be tolerated, the patient may have their dose reduced to 50 mg once daily.

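### For early discontinuers, the care-plan compliance rule in SAP 7.5 omits the deduction for instructed dose reductions and pauses, so read as written it equals ordinary compliance

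*SAP*

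**What the plan says.** SAP 7.5 (Drug Exposure, at-home part) derives two compliance percentages from ampoule counts.

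- **Ordinary compliance.** The denominator is the "total number of ampoules that would be used if they were fully dosing for the number of days between visits". For early discontinuers, "the denominator will be the total number of ampoules, which would be used up to, and including the date of discontinuation".
- **Care-plan compliance.** The denominator starts from the same full-dosing term and is then reduced: "minus the number of ampoules that would be missed if following instructions to reduce or interrupt dose". That subtraction is the only difference from the ordinary measure. The sentence on early discontinuation follows in identical words: "If a subject discontinues early, the denominator will be the total number of ampoules, which would be used up to, and including the date" (the day the patient stops). The subtraction is not repeated.

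For both measures, "The percent compliance will be categorized" into five bands (≥80%, 60 to <80%, 40 to <60%, 20 to <40%, <20%) and tabulated by treatment group.

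Protocol 8.7 describes the instructions that the care-plan measure is meant to recognise. It recommends that sites "reduce the 100 mg twice daily dose to 50 mg twice daily if the patient cannot tolerate the 100 mg dose", with a further step to 50 mg once daily. It also covers stopping for intolerance and restarting on improvement, without naming a regimen.

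**The concern.** The care-plan measure exists to avoid counting an instructed reduction or pause as missed drug. Its rule for early discontinuers appears to have been carried over from the ordinary bullet, and as written it takes that credit away. Patients who reduce or pause for intolerance and then stop are a foreseeable group in a study whose primary objective is tolerability: Protocol 8.7 provides for the reduction or pause, and 8.6 for discontinuation if symptoms persist. For them the table would not separate missed doses from doses withheld on instruction, and some would appear in a lower compliance band than their behaviour warrants.

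**Working it through.** The plan states no figure for this point, so there is nothing of its own to reproduce. The check is arithmetic on the ampoule counts.

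**Inputs**

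- 100 mg twice daily uses 4 ampoules a day (Protocol 8.3.5: "2 pouches per day; 2 ampoules per twice daily dose").
- 50 mg once daily uses 1 a day (Protocol 8.3.5: "1/2 pouch per day; 1 ampoule per once daily dose").
- It follows that 50 mg twice daily uses 2 a day and a pause uses 0.
- Supply check: a carton holds 18 × 2 = 36 ampoules. Over 28 days, 28/36 = 0.78 and 112/36 = 3.11 cartons, which round up to the protocol's one and four.
- Assumptions: the patient follows every instruction exactly, and the numerator is the true number used. The documents give no timings or frequencies for reductions, pauses or discontinuations, so the days below are illustrative.

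**Formulas.** Let *a* be the full-dose ampoules per day, *D* the days to discontinuation, *U* the ampoules used and *M* the ampoules omitted on instruction.

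- As written for a discontinuer: 100 × U / (a × D)
- With the deduction: 100 × U / (a × D − M)

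With full adherence U = a × D − M, so the second formula always gives 100%.

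| Instructed pattern, then discontinuation | U | a × D | As written | Band | With deduction |
|---|---|---|---|---|---|
| 4/day for 14 days, 2/day for 42 days | 56 + 84 = 140 | 4 × 56 = 224 | 62.5% | 60 to <80% | 140/140 = 100% |
| Full dose, 14-day pause in 56 days (1/day) | 42 | 56 | 75.0% | 60 to <80% | 100% |
| 4/day for 28 days, 2/day for 56 days | 112 + 112 = 224 | 4 × 84 = 336 | 66.7% | 60 to <80% | 100% |
| 4/day, 2/day, 1/day, 28 days each | 112 + 56 + 28 = 196 | 336 | 58.3% | 40 to <60% | 100% |
| 4/day for 56 days, 2/day for 28 days | 224 + 56 = 280 | 336 | 83.3% | ≥80% | 100% |
| Full dose, 14-day pause in 84 days (1/day) | 70 | 84 | 83.3% | ≥80% | 100% |
| Full dose, 28-day pause in 84 days (1/day) | 56 | 84 | 66.7% | 60 to <80% | 100% |

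The pause rows give the same percentages at 4 ampoules a day, because the rate cancels.

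**When the band changes.** If a share *s* of the time is spent at a fraction *r* of full dose, the as-written score is 1 − s(1 − r). It falls below 80% when s > 0.2/(1 − r):

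- 50 mg twice daily (r = 0.5): more than 40% of the time.
- 50 mg once daily after 100 mg twice daily (r = 0.25): more than 26.7%.
- Paused (r = 0): more than 20%.

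Reduction alone cannot take the score below 50% (50 mg twice daily) or 25% (50 mg once daily).

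**Contrast with a patient who does not discontinue.** Take a reduction to 2 a day from Day 29 through Day 168. U = 112 + 280 = 392 and full dosing is 672. Ordinary compliance is 392/672 = 58.3%. Care-plan compliance is 392/(672 − 280) = 100%. Here the two measures separate as intended; only the discontinuation sentence makes them coincide.

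**The case against.** The best defence is textual. The discontinuation sentence does not itself mention full dosing. Its evident purpose is to end the counting period at discontinuation, and inside the care-plan bullet the ampoules that would be used could mean those due under the care plan. That reading is possible. It requires one sentence to carry two meanings in adjacent bullets, since in the ordinary bullet it can only mean full dosing. The two programs that could be written from it give different results.

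Three stronger inferences are tempting, and the documents do not support them.

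- **That these patients are classed as non-compliant.** SAP 7.5 has five descriptive bands and no non-compliance cut-off. The per-protocol exclusions in SAP 5.3 name study drug deviations but no compliance percentage. Under the protocol, entry to Part B and removal for non-compliance rest on the investigator's judgement.
- **That the distortion falls mainly on the 100 mg arm.** The stepwise reductions are written only for that regimen, so some tilt is plausible. Pauses name no regimen and lower the percentage equally in both. Patients randomized to 50 mg and converted in Part B come under the same reduction steps. Nothing in the documents shows how often reduced or paused patients go on to discontinue.
- **That the table could have steered the choice of regimen.** Protocol 8.2 mentions compliance as a consideration in choosing which regimens to test, not as a selection criterion applied to this table. The DSMB recommended 100 mg twice daily on 12 October 2020 on an FVC trend. SAP version 3.0 is dated 15 July 2021, so tables produced under it could not have informed that step.

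It also stands that patients who do not discontinue, and discontinuers with no instructed reduction or pause, are unaffected, and that the accountability data are listed in full.

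**Conclusion.** The point holds as a defect in a derivation rule with limited reach. As written, care-plan compliance equals ordinary compliance for every early discontinuer, so a fully adherent patient who was reduced or paused scores below 100%. In the illustrations the score is 58.3% to 83.3%, usually one band below the top and two bands below with a second reduction step; a late reduction or short pause leaves the patient in the top band. This rests on the literal reading, on exact adherence and on assumed timings. The number of patients affected equals those reduced or paused who later discontinued, which the documents do not give. The consequence is confined to the descriptive compliance tables; no endpoint, model or analysis set uses the percentage.

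**What to change.** In the second compliance bullet of SAP 7.5, replace the discontinuation sentence with one to this effect: for a patient who stops early, take the ampoules due at full dose through the discontinuation date and subtract those the patient was told to omit through that same date. The ordinary-compliance bullet can stay as it is.

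The cost is one SAP sentence and one line of derivation. The records of instructed reductions and pauses are already needed for patients who do not discontinue, so no new data are required. If the sponsor always intended the deduction to apply, the change only makes that explicit.

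A separate matter should be settled before either measure is computed: SAP 7.5 counts used ampoules that are returned, whereas Protocol 8.8.1 has patients discard used ampoules and bring back unused ones. Correcting the denominator does not resolve that.
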